10.1.2 Secondary Endpoint

To determine preliminary efficacy, response (defined as having at least PR in evaluable patients) will be reported as a proportion and 95% confidence interval using exact binomial methods. Given that this is a purely descriptive protocol, there is no set hypothesis regarding the response rate. Proportions for clinical response (defined as having at least PR or stable disease) will also be calculated. Please refer to appendices for detailed explanations of the clinical response criteria for each population.

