Appendix I – International Working Group Response Criteria for AML

Definitions of response criteria are based primary on those given by Cheson et al.

Category	Definition
Complete remission (CR) ¹	Bone marrow blasts <5 percent; absence of blasts with Auer rods; absence of extramedullary disease; absolute neutrophil count >1.0 x 10 ⁹ /L (1000/μL); platelet count >100 x 10 ⁹ /L (100,000/μL); independence of red cell transfusions
CR with incomplete recovery (CRi) ²	All CR criteria except for residual neutropenia (<1.0 x 10 ⁹ /L (1000/μL)) or thrombocytopenia (<100 x 10 ⁹ /L (100,000/μL))
Morphologic leukemia-free state ³	Bone marrow blasts <5%; absence of blasts with Auer rods; absence of extramedullary disease; no hematologic recovery required.
Partial remission (PR)	All hematologic criteria of CR; decrease of bone marrow blast percentage to 5 to 25%; and decrease of pretreatment bone marrow blast percentage by at least 50%.
Cytogenic CR (CRc) ⁴	Reversion to a normal karyotype at the time of morphologic CR (or CRi) in cases with an abnormal karyotype at the time of diagnosis; based on the evaluation of 20 metaphase cells from bone marrow.
Molecular CR (CRm) ⁵	No standard definition; depends on molecular target.
Treatment failure	
Resistant disease (RD)	Failure to achieve CR, CRi or PR; only includes patients surviving ≥7 days following completion of initial treatment, with evidence of persistent leukemia by blood and/or bone marrow examination.
Death in aplasia	Deaths occurring ≥ 7 days following completion of initial treatment while cytopenic; with an aplastic or hypoplastic bone marrow obtained within 7 days of death, without evidence of persistent leukemia.
Death from indeterminate cause	Deaths occurring before completion of therapy, or <7 days following its completion; or deaths occurring ≥7 days following completion of initial therapy with no blasts in the blood, but no bone marrow examination available.
Relapse ⁶	Bone marrow blasts ≥ 5%; or reappearance of blasts in the blood; or development of extramedullary disease.

¹ All criteria need to be fulfilled; marrow evaluation should be based on a count of 200 nucleated cells in an aspirate with spicules; if ambiguous, consider repeat exam after 5 to 7 days; flow cytometric evaluation may help to distinguish between persistent leukemia and regenerating normal marrow; a marrow biopsy should be performed in cases of dry tap, or if no spicules are obtained; no minimum duration of response required.

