Appendix II – Revised IWG-MRT & ELN Response Criteria for MF

The criteria below are a revision of the International Working Group-Myeloproliferative Neoplasms Research and Treatment (IWG-MRT) criteria for treatment response in myelofibrosis (MF) and represents a collaborative effort by the IWG-MRT and the European LeukemiaNet to objectively assess the value of new drugs in inducing morphologic remission or improvement in MF-associated symptomatic burden (MF-SB).

Response Categories	Required Criteria ¹
CR (complete remission)	
 Bone marrow²: age-adjusted normocellularity; < 5% blasts; ≤ grade 1 MF³ Peripheral blood: hemoglobin ≥ 100 g/L and < ULN; neutrophil count ≥ 1 × 10⁹ and < ULN Platelet count ≥ 100 × 10⁹ and < ULN; < 2% immature myeloid cells⁴ Clinical: resolution of disease symptoms; spleen and liver not palpable; no evidence of EMH.
PR (partial remission)	
 Peripheral blood: hemoglobin ≥100 g/L and <UNL; neutrophil count ≥1 × 10⁹/L and <UNL; platelet count ≥100 × 10⁹/L and <UNL; <2% immature myeloid cells⁴ and Clinical: Resolution of disease symptoms; spleen and liver not palpable; no evidence of EMH or Bone marrow²: Age-adjusted normocellularity; <5% blasts; ≤grade 1 MF³, and peripheral blood: Hemoglobin ≥85 but <100 g/L and <UNL; neutrophil count ≥1 × 10⁹/L and <UNL; platelet count ≥50, but <100 × 10⁹/L and <UNL; <2% immature myeloid cells⁴ and Clinical: Resolution of disease symptoms; spleen and liver not palpable; no evidence of EMH
Clinical improvement (CI)	The achievement of anemia, spleen or symptoms response without progressive disease or increase in severity of anemia, thrombocytopenia, or neutropenia ⁵
Anemia response	
 Transfusion-independent patients: a ≥ 20 g/L increase in hemoglobin level⁶ Transfusion-dependent patients: becoming transfusion independent⁷
Spleen response ⁸	
 A baseline splenomegaly that is palpable at 5-10 CM, below the LCM, becomes not palpable⁹ 
OR
 
 A baseline splenomegaly that is palpable at > 10 cm, below the LCM, decreases by ≥ 50% 
A baseline splenomegaly that is palpable at <5 cm, below the LCM, is not eligible for spleen response

Symptoms response	A ≥ 50% reduction in the MPN-SAF TSS ¹⁰

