Progressive disease ¹¹	
 Appearance of a new splenomegaly that is palpable at least 5 cm below the LCM or A ≥100% increase in palpable distance, below LCM, for baseline splenomegaly of 5-10 cm or A 50% increase in palpable distance, below LCM, for baseline splenomegaly of >10 cm or Leukemic transformation confirmed by a bone marrow blast count of ≥20% or A peripheral blood blast content of ≥20% associated with an absolute blast count of ≥1 × 10⁹/L that lasts for at least 2 weeks
Stable disease	Belonging to none of the above listed response categories.

Relapse	
 • No longer meeting criteria for at least CI after achieving CR, PR, or CI, or • Loss of anemia response persisting for at least 1 month or • Loss of spleen response persisting for at least 1 month
Recommendations for assessing treatment-induced cytogenetic and molecular changes	
Cytogenetic remission	
 • At least 10 metaphases must be analyzed for cytogenetic response evaluation and requires confirmation by repeat testing within 6 months window 
CR: eradication of a preexisting abnormality PR: ≥50% reduction in abnormal metaphases
 
Partial response applies only to patients with at least ten abnormal metaphases at baseline.

Molecular remission	
 • Molecular response evaluation must be analyzed in peripheral blood granulocytes and requires confirmation by repeat testing within 6 months window • CR: Eradication of a pre-existing abnormality • PR: ≥50% decrease in allele burden 
Partial response applies only to patients with at least 20% mutant allele burden at baseline.

Cytogenetic/molecular relapse	Re-emergence of a pre-existing cytogenetic or molecular abnormality that is confirmed by repeat testing.

EMH, extramedullary hematopoiesis (no evidence of EMH implies the absence of pathology- or imaging study-proven nonhepatosplenic EMH); LCM, left costal margin; UNL, upper normal limit.

¹ For all response categories, benefit must last for ≥12 wk to qualify as a response.

² Baseline and posttreatment bone marrow slides are to be interpreted at one sitting by a central review process. Cytogenetic and molecular responses are not required for CR assignment.

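### Clinical response counts stable disease in both diseases, but Appendix I has no such category for AMKL; in MF, Clinical Improvement is not placed and its printed platelet minimum cannot be met

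*Combined protocol and SAP*

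**What the plan says.** Section 10.1.2 states: "Proportions for clinical response (defined as having at least PR or stable disease) will also be calculated". It adds: "Please refer to appendices for detailed explanations of the clinical response criteria for each population". The Study Summary repeats the definition. Neither place restricts it to one disease.

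**AMKL, Appendix I.** The rows are CR, CRi, morphologic leukemia-free state, PR, cytogenetic CR, molecular CR, three kinds of treatment failure, and relapse. Resistant disease, the first kind of treatment failure, is described as "Failure to achieve CR, CRi or PR" in patients who survive at least 7 days after initial treatment, "with evidence of persistent leukemia by blood and/or bone marrow examination". PR needs "All hematologic criteria of CR; decrease of bone marrow blast percentage" to a stated range. Morphologic leukemia-free state is listed above PR, with "no hematologic recovery required".

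**MF, Appendix II.** CI is a category of its own: "The achievement of anemia, spleen or symptoms response without progressive disease" or worsening cytopenia. Anemia, spleen and symptoms responses also have their own rows. Stable disease is the remainder: "Belonging to none of the above listed response categories". Footnote 5 adds a platelet minimum for CI, printed as 25 000 × 10⁹/L, and a neutrophil minimum of 0.5 × 10⁹/L.

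**The concern.** A derived endpoint has to be computable from the criteria it cites. Here one definition is laid over two classification systems and fits neither cleanly.

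For AMKL, stable disease would have to be defined by someone after the data are in. For MF, a patient with a documented spleen, anemia or symptoms response could be left out of clinical response while a patient with no change is counted in. The platelet minimum that gates CI is also printed at a level no patient can reach. At stake are the AMKL clinical-response proportion, the MF CI count and, depending on the reading, the MF clinical-response proportion.

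**Working it through.** No sample-size or power figure lies behind this point. The check is a row-by-row reading, a unit conversion, and the weight of one patient.

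**1. AMKL categories against the definition.**
- CR and PR: at least PR, clearly.
- Persistent leukemia in a survivor without CR, CRi or PR: Resistant disease, under Treatment failure. No row separates stable from progressing patients within this group.
- CRi: the Resistant disease row groups it with CR and PR. Footnote 2 of Appendix I puts it with CR in the overall remission rate, but only for intensified or double induction protocols, which this trial is not.
- Morphologic leukemia-free state: needs no count recovery, whereas PR needs all the hematologic criteria of CR. Footnote 3 says the category may be useful in phase I trials of novel agents. Nothing ranks it against PR.

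So the stable-disease part cannot be assigned, and the PR-or-better part is unsettled for two categories.

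**2. The CI platelet minimum.** Appendix I gives the conversion: 100 × 10⁹/L = 100,000/µL, a factor of 1000. The hydroxyurea note in 3.3.2 agrees: 1 million = 1000 × 10⁹/L.
- As printed: 25 000 × 1000 = 25,000,000/µL.
- Against the CR floor of 100 × 10⁹/L: 25 000 / 100 = 250 times.
- Against the lower PR floor of 50 × 10⁹/L (marrow route): 25 000 / 50 = 500 times.
- Against the 1000 × 10⁹/L hydroxyurea level: 25 000 / 1000 = 25 times.

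The neutrophil minimum in the same sentence is on an ordinary scale, so the fault lies in the platelet figure alone. If 25 × 10⁹/L was meant, that is 25,000/µL, a figure also used in 4.3.1 for another purpose. This is an inference; no section states it for CI.

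**3. Where MF improvers go.**

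| Footnote 5 | Category of an improver | Clinical response under the literal definition |
|---|---|---|
| As printed | Not CI; either stable disease or still under the anemia, spleen or symptoms row | Ambiguous |
| Corrected | CI: not PR, not residual stable disease | Not named |

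Appendix II's Relapse row speaks of losing at least CI after CR, PR or CI. That ranks CI below PR and makes *stable disease or better* the natural reading.

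**4. Weight of one patient.** The shift is 1/n, at the sizes used for the standard errors in 10.2: 1/24 = 4.2 points, 1/18 = 5.6, 1/12 = 8.3, 1/6 = 16.7. These are scenarios rather than planned arm sizes, and evaluable patients may be fewer.

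**5. Illustration for AMKL (assumption).** Section 1.6 cites 13% response and 49% stable disease for alisertib in relapsed and refractory AML, and says AMKL patients were unlikely to be among them. If those rates applied, clinical response would be about 13% with stable patients classed as resistant, and 13 + 49 = 62% with them counted. In whole patients that is 1/6 against 4/6, or 2/12 against 7/12.

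**The case against.** The strongest reply is that this is a descriptive secondary endpoint with no hypothesis, that nobody would apply a threshold of 25 million platelets per microliter, and that *stable disease or better* is how any reader would take the definition. Under that reading, the misprint changes the CI count but not the MF clinical-response proportion. All of this is fair, and it keeps the point minor. The multiples of 250 and 500 show that the figure is a misprint; they do not measure an effect on results.

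A second reply is that Section 2.2 reports best response by category, so counts can be regrouped later. That works for MF. It does not work for AMKL, because no reported category separates stable from progressing disease within Resistant disease.

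Three stronger readings are tempting and are not supported:
- That the misprint necessarily turns improvers into stable disease. Appendix II lists anemia, spleen and symptoms responses as separate rows above stable disease, so such a patient may still belong to a listed row.
- That CRi is placed only by the Resistant disease row. Footnote 2 of Appendix I also addresses it, conditionally.
- That the whole repair is wording on data already collected. An AMKL stable-disease rule would need a progression definition that Appendix I lacks. For MF, footnote 11 of Appendix II requires MRI or CT to confirm splenomegaly progression, while the schedule in 5.1 lists no imaging and footnote 9 relies on palpation, or ultrasound where needed, for response.

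**Conclusion.** The point holds, as a minor defect. The AMKL clinical-response proportion cannot be derived from the criteria it cites, and the standing of CRi and morphologic leukemia-free state against PR is open. The CI platelet minimum is wrong as printed and would leave that category empty. Once it is corrected, the definition omits CI on a literal reading, though that is probably not what is meant.

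The size is one patient in n for each reclassification: 4.2 points at 24, up to 16.7 at 6. The AMKL effect is nil if no AMKL patients enroll, which 10.2 accepts. The MF effect is nil if no patient improves without reaching PR, or if CI is counted as better than stable disease. The primary safety endpoint and the MF proportion with at least PR are unaffected. A reader might infer that the efficacy results as a whole are unreliable; the documents do not support that.

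**What to change.** - Check Appendix II footnote 5 against the source criteria and reconcile the platelet unit.
- In 10.1.2 and the Study Summary, define MF clinical response as CR+PR+CI+SD.
- Limit clinical response to MF. Report AMKL by Appendix I category, and state whether CRi and morphologic leukemia-free state count as at least PR.
- Reconcile footnote 11's imaging requirement with the palpation-based approach, so that the split between stable and progressive disease in MF can be made from what is collected.

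The first three are changes of wording and one figure. The price is that AMKL loses a disease-control proportion, which the cited criteria cannot support anyway. The fourth needs a decision by the study team. Keeping the AMKL proportion would cost more, since stable disease and progression would both have to be defined for that group before the data are reviewed.

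### Read literally, the MF clinical response rate leaves out Clinical Improvement, so it falls when a stable patient improves

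*Combined protocol and SAP*

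**What the plan says.** Section 10.1.2 defines the first efficacy measure as follows: "response (defined as having at least PR in evaluable patients) will be reported as a proportion and 95% confidence interval using exact binomial methods". It then adds the second: "Proportions for clinical response (defined as having at least PR or stable disease) will also be calculated". The Study Summary gives the same two definitions. For the criteria, Section 10.1.2 sends the reader elsewhere: "Please refer to appendices for detailed explanations of the clinical response criteria for each population".

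For MF that means Appendix II. It lists CR, then PR, then Clinical Improvement, which I abbreviate CI here, as the protocol does; confidence intervals are written out as intervals. CI is defined as "The achievement of anemia, spleen or symptoms response without progressive disease or increase in severity of anemia, thrombocytopenia, or neutropenia". The appendix then defines the three component responses; the symptoms response, for example, is a drop of at least "50% reduction in the MPN-SAF TSS". Progressive disease and stable disease come after these, and stable disease is "Belonging to none of the above listed response categories". Relapse is defined partly as "No longer meeting criteria for at least CI after achieving CR, PR, or CI", which makes CI a level of response below CR and PR.

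Sections 2.2 and 6.2 have responses categorised by these criteria and reported for evaluable patients. Section 10.1.3 summarises spleen size and the MPN-SAF score descriptively, as exploratory endpoints for the MF arm.

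**The concern.** An efficacy proportion should not go down when patients do better. The two definitions in Section 10.1.2 name PR and stable disease, but in MF there is a category between them that they do not name. If CI falls into neither proportion, a patient with a qualifying spleen, anemia or symptoms response is counted like a patient who progressed, and the clinical response rate penalises that improvement.

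The gap matters because preliminary efficacy in each population is the secondary objective, and because Section 10.2 accepts a sample made up entirely of MF patients. It could therefore touch all of the trial's efficacy data. It does not arise in AMKL, because Appendix I has no CI category.

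**Working it through.** The plan gives no expected clinical response rate, so there is no stated figure to reproduce. The check maps the categories first and then illustrates the size.

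**Step 1: place each MF category in the two proportions.** The inputs are the two definitions in Section 10.1.2 and the category definitions in Appendix II.

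- CI is not at least PR. It is listed separately after PR, and the relapse definition orders it below CR and PR. The CR row asks for "Clinical: resolution of disease symptoms; spleen and liver not palpable; no evidence of EMH", and both routes to PR impose the same clinical requirement along with blood-count limits. A patient can meet CI without meeting these.
- CI is not stable disease. Stable disease is what remains after every category listed above it, and CI is one of those.

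| MF category | Response (at least PR) | Clinical response, read literally |
|---|---|---|
| CR | 1 | 1 |
| PR | 1 | 1 |
| CI | 0 | 0 |
| Stable disease | 0 | 1 |
| Progressive disease | 0 | 0 |

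On response, CI and stable disease tie at 0. On clinical response, CI scores below stable disease and level with progression.

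**Step 2: effect of one patient.** Moving one patient from stable disease to CI, with n evaluable MF patients, changes clinical response by −1/n. At the maximum n = 24 this is −1/24 = −4.2 percentage points. With 12 it would be −1/12 = −8.3 points.

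**Step 3: an illustration.** The documents give no expected counts, so these are assumed: 24 evaluable MF patients with 0 PR, 6 CI, 12 stable and 6 progressive, and all Appendix II conditions for CI met. Intervals are Clopper-Pearson, the exact binomial method: lower limit = Beta quantile (0.025; x, n−x+1), upper limit = Beta quantile (0.975; x+1, n−x).

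- Response, CR+PR: 0/24 = 0% (0 to 14.2%)
- Clinical response as written, (0+12)/24 = 12/24 = 50% (29.1 to 70.9%)
- Clinical response with CI, (0+6+12)/24 = 18/24 = 75% (53.3 to 90.2%)
- CR+PR+CI: 6/24 = 25% (9.8 to 46.7%)

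**Step 4: the range.** Now assume 1 PR and 8 progressive, with the other 15 of 24 divided between CI and stable disease.

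| CI | Stable | Clinical response as written | Clinical response with CI | CR+PR+CI |
|---|---|---|---|---|
| 0 | 15 | 16/24 = 66.7% | 16/24 = 66.7% | 1/24 = 4.2% |
| 4 | 11 | 12/24 = 50.0% | 16/24 = 66.7% | 5/24 = 20.8% |
| 8 | 7 | 8/24 = 33.3% | 16/24 = 66.7% | 9/24 = 37.5% |
| 10 | 5 | 6/24 = 25.0% | 16/24 = 66.7% | 11/24 = 45.8% |

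Response (at least PR) stays at 1/24 = 4.2% throughout. The gap equals the number of CI patients divided by n, and is zero if there are none. Down the table more patients improve, yet the rate as written falls.

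**The case against.** The strongest reply is that the phrase sets a floor: *at least* governs both terms, and the authors meant stable disease or better. CI would then count. That may well be the intent, and Appendix II does treat CI as a positive level. But this reading makes the mention of PR redundant, and neither Section 10.1.2, the Study Summary nor the endpoint sections state it. Two analysts could report different rates from the same data.

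A second reply is that the information is not lost. This is largely right. A reader might infer that the plan cannot show spleen or symptom benefit at all, and the documents do not support that. Sections 2.3.3, 2.3.4 and 10.1.3 provide descriptive summaries of spleen size and MPN-SAF score, and best response is reported by category under Section 2.2, so a CI count should be recoverable. What is missing is narrower: no planned responder proportion includes CI, and no analysis of anemia response is planned.

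Third, a strict CR+PR response rate is a legitimate choice, and the study is descriptive with no hypothesis on response. Both points stand. The first is why CR+PR should be kept. The second means there is no error-rate problem, but in a descriptive study the reported proportion is the result and still needs a coherent definition.

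Finally, a reader might infer from the eligibility criteria that most MF benefit would appear as CI. The documents give no expected distribution of responses, and Section 1.6 says alisertib has not been studied in MF. The point does not rely on that inference.

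**Conclusion.** The definition of clinical response needs correcting for MF. Taken as written with Appendix II, it leaves CI out of both efficacy proportions and makes the clinical response rate fall as stable patients improve to CI. The size runs from 0 points with no CI patients to 4.2 points for each CI patient at n = 24; it is 25 points in the illustration with 6.

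Three limits apply. A reader might infer that CI ranks below stable disease on every measure, but the two tie at 0 on response and the inversion is confined to clinical response. The result rests on the literal reading; under stable disease or better the rate would be right, but the text would still need to say so. And the counts are assumptions. A patient qualifies as CI only if the benefit lasts at least 12 weeks, without progression or worsening cytopenias and with the minimum platelet and neutrophil counts. A patient who fails one of these without progressing, and meets no other category, would be stable disease and would count in clinical response.

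This is a secondary, untested endpoint in a safety pilot. The correction is worth making because it is specific, nearly free, and best settled before the data are analysed.

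**What to change.** In Section 10.1.2 and the Study Summary, for MF:

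1. Define clinical response as CR, PR, CI or stable disease under Appendix II. This alone repairs the definition.
2. Keep CR+PR as the response rate. Report CR+PR+CI beside it with its exact 95% interval, labelled as an added descriptive proportion.

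Separate responder rates for anemia, spleen and symptoms are optional and not needed for the correction.

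The cost is a wording change in two places and one extra reported proportion. Blood counts, palpation and MPN-SAF are already in the MF schedule (Section 5.1). The exception is CI that rests on anemia response in a transfusion-dependent patient. Appendix II then needs red-cell transfusion history for the 12 weeks before enrolment and a 12-week transfusion-free interval on treatment. Transfusions have no row of their own in the schedule, so the sponsor should state which records will supply them.
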